Attachment 6: SNOT-22 Survey**SNOT22 Survey**

	No problem	Problem as bad as it can be				
		Severe Problem	Moderate Problem	Mild or slight problem	Very mild problem	→
2. Considering how severe the problem is when you experience it and how frequently it happens, please rate each item below on how "bad" it is by circling the number that corresponds with how you feel using this scale: →						
1. Need to blow nose	0	1	2	3	4	5
2. Sneezing	0	1	2	3	4	5
3. Runny nose	0	1	2	3	4	5
4. Cough	0	1	2	3	4	5
5. Post-nasal discharge	0	1	2	3	4	5
6. Thick nasal discharge	0	1	2	3	4	5
7. Ear fullness	0	1	2	3	4	5
8. Dizziness	0	1	2	3	4	5
9. Ear pain	0	1	2	3	4	5
10. Facial pain/pressure	0	1	2	3	4	5
11. Difficulty falling asleep	0	1	2	3	4	5
12. Wake up at night	0	1	2	3	4	5
13. Lack of a good night's sleep	0	1	2	3	4	5
14. Wake up tired	0	1	2	3	4	5
15. Fatigue	0	1	2	3	4	5
16. Reduced productivity	0	1	2	3	4	5
17. Reduced concentration	0	1	2	3	4	5
18. Frustrated/restless/irritable	0	1	2	3	4	5
19. Sad	0	1	2	3	4	5

20. Embarrassed	0	1	2	3	4	5
21. Loss of smell or taste	0	1	2	3	4	5
22. Nasal obstruction	0	1	2	3	4	5

Attachment 7: 5-Week Follow Up**FOLLOW UP 5 WEEKS**

OVER THE LAST WEEK, HOW TROUBLESOME HAVE THE FOLLOWING SYMPTOMS BEEN? PLEASE PLACE A MARK ON THE LINE.		
	Not troublesome	Worst thinkable/troublesome
Nasal blockage/obstruction/congestion	◆————◆	◆————◆
Nasal discharge/drainage out of the front or back of nose	◆————◆	◆————◆
Pain/pressure in nose or sinuses	◆————◆	◆————◆
Sense of smell	◆————◆	◆————◆
OVERALL ASSESSMENT OF NASAL AND SINUS PROBLEMS	◆————◆	◆————◆

Change in nasal symptoms and use of device

Please rate changes in your nasal symptoms and use of device.

Symptom	None	Mild	Moderate	High
Improvement in nasal obstruction/stuffiness	0	1	2	3
Improvement in nasal drainage/discharge	0	1	2	3
Improvement in nasal or sinus pressure	0	1	2	3
Improvement in ability to smell	0	1	2	3
Use of the Device				
Pain with use of device	None	Mild	Moderate	Severe
Comfort and ease of use	Poor	Low	Moderate	High
Bleeding:	Yes	No		
Willingness to use again	Yes	No		
Willingness to recommend to friend/family	Yes	No		

Total Nasal Symptom Score

Please answer all questions to the best of your ability. This information will assist us in understanding and treating symptoms. Please rate how your symptoms have been over the **past week**.

Symptom	None	Mild: Symptom clearly present but easily tolerated	Moderate: Symptom bothersome but tolerable	Severe: Symptom difficult to tolerate – interferes with activities
Nasal congestion/obstruction	0	1	2	3
Runny nose/secretions	0	1	2	3
Nasal itching	0	1	2	3
Sneezing	0	1	2	3
Sleep difficulty with nasal symptoms	0	1	2	3

NOSE Scale

Please help us to better understand the impact of nasal obstruction on your quality of life by completing the following survey. Thank you!

Over the past **ONE month**, how much of a problem were the following conditions for you?

	Not a problem	Very mild problem		Moderate problem	Fairly bad problem	Severe problem
Nasal congestion or stuffiness	0	1		2	3	4
Nasal blockage or obstruction	0	1		2	3	4
Trouble breathing through my nose	0	1		2	3	4
Trouble sleeping	0	1		2	3	4
Unable to get enough air through my nose during exercise or exertion	0	1		2	3	4

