1.0 Objectives / Specific Aims

- Primary: To determine the safety and efficacy of a single SinuSonic intervention.
- Secondary: Secondary objectives of this study is to determine:
 - the safety and efficacy of a twice daily SinuSonic intervention over 2 weeks.
 - the safety and efficacy of a twice daily SinuSonic intervention over 4 to 6 weeks.

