number of antibiotics have been approved for the treatment of acute sinusitis; however, there is no conclusive evidence that oral antibiotics, topical antibiotics, or topical antifungal agents are effective in the treatment of chronic sinusitis, and their use remains controversial, particularly due to concerns over emerging resistance (Ebbens 2006; Fokkens 2007; Videler 2008). As chronic sinusitis is characteristically an inflammatory disease, the anti-inflammatory effects of corticosteroids could be expected to be of benefit. There are no clinical studies published on the use of systemic corticosteroids for the treatment of chronic sinusitis without polyps, although there is evidence that systemic corticosteroids are effective at reducing the size of nasal polyps and improving rhinitis symptoms (Fokkens 2007; Van Zele 2010). Medical treatment with nasal corticosteroids (as currently available for treatment of rhinitis) is considered a first step in the treatment of chronic sinusitis; however, the data on sprays or drops does not suggest they are very effective.

Patients with chronic sinusitis currently have limited medical options for treatment and no medication is approved for the treatment of chronic sinusitis. Standard nasal spray pumps suffer from a number of drawbacks and they are considered suboptimal for reliable drug delivery to target sites beyond the nasal valve (Aggarwal 2004). Current congestion medications are not always fully effective. This study aims to test the safety and efficacy of the SinuSonic device on adults with moderate to severe nasal congestion. SinuSonic is a medical device that utilizes sound and pressure combined with normal breathing to relieve nasal congestion. The study will take place over the course of 4 to 6 weeks starting with a baseline assessment. This study will use patient responses to measure how effective SinuSonic devices are in treating adults with moderate to severe congestion in adults.

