3.0 Intervention to be studied

- Initial intervention: Subjects will use the SinuSonic device for 3 minutes in the clinic setting.
- Secondary intervention: Subjects will use SinuSonic device twice daily for 3 minutes in the home setting for 14 days.
- Tertiary intervention: Subjects will continue to use the SinuSonic device twice daily for 3 minutes in the home setting for 2-4 weeks.

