4.0 Inclusion and Exclusion Criteria/ Study Population

The study population will consist of individuals present for care at the Otolaryngology clinics at the Medical University of South Carolina with nasal congestion, friends/family members of patients presenting for care at MUSC’s Otolaryngology clinics.

Inclusion Criteria

- Adults \geq 18 years of age
- Complaints of nasal congestion present for 2 weeks or more and a qualifying nasal congestion score of >5 (10 point VAS scale).

Exclusion Criteria

- Fixed structural cause of nasal congestion (moderate or severe septal deviation, moderate or severe nasal valve collapse, Grade 3-4 polyp)
- Inability to read and understand English
- Allergic sensitivity to silicone or any other component of device
- History of severe nose bleeding within last 3 months
- Anticoagulation (Aspirin ok)
- Known pregnancy
- Current nasal crusting or ulceration revealed on rhinoscopy
- Inability to perform treatment due to underlying medical condition

- Topical decongestant use in last week

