6.0 Setting

Research will be conducted at the Medical University of South Carolina. Potential participants screening as well as the 2-week post treatment assessment will take place in the outpatient sinus clinics. The 4-6 week assessment will be done via emailing of surveys.

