19.0 DATA SAFETY MONITORING AND REPORTING

Safety data listings will be reviewed by Principal Investigator, Co-Investigators, and the research team at regular intervals throughout the study.

Safety will be monitored throughout the study based on monitoring of adverse events, performing nasal exams, measuring vital signs (ie blood pressure, pulse) and weight, and through collection of concomitant medication information.

The period of observation for collection of non-serious adverse events extends from the time the subject gives informed consent until completion of the End-of-study visit or Early Termination Visit. Serious adverse events (SAE) will be reported to the MUSC IRB and to the sponsor from the time of informed consent through 30 days after the last use of the SinuSonic. Adverse event data listings will be reviewed by the principal investigator, co-investigators, and the research team at regular intervals throughout the study.

All AEs, regardless of seriousness or relationship to SinuSonic use, spanning from the signature of the informed consent form until the end of the study as defined by the protocol for that patient, are to be reported to the Healthy Humming, LLC. All AEs which follow the MUSC IRB qualifications will also be reported to the MUSC IRB within 24 hours of site knowledge of the event.

The Investigator will take appropriate measures to follow all AEs until clinical recovery is complete and laboratory results have returned to normal, or until progression has been stabilized, or until death, in order to ensure the safety of the patients. This may imply that observations will continue beyond the last planned visit per protocol, and that additional investigations may be requested by the monitoring team up to as noticed by Healthy Humming, LLC.

In the case of occurrence of an SAE, the Investigator will immediately (within 24 hours) report the event to Healthy Humming, LLC and to the MUSC IRB, as applicable.

References

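### After week 2 the only scheduled contact is an emailed form with two device-harm items and no open adverse-event question, so the 4-6 week safety summary is likely to under-count other non-serious events

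*Combined protocol and SAP*

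**What the plan says.** Section 1.0 lists as a secondary objective "the safety and efficacy of a twice daily SinuSonic intervention over 4 to 6 weeks". Section 10.0 plans a summary of safety data at each time point. On reporting, Section 19.0 covers "All AEs, regardless of seriousness or relationship to SinuSonic use", from consent to the end of the study for that patient. Sections 9.0, 11.0 and 19.0 also say that safety is monitored throughout by AE monitoring, nasal examination, vital signs, weight and concomitant medication.

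Section 9.1 shows one assessment after week 2, visit 4. Section 6.0 says how it is done: "The 4-6 week assessment will be done via emailing of surveys". In Section 9.1, rhinoscopy is marked at screening and week 2 only, vital signs at screening only, and there is no row for AEs or concomitant medication at any visit.

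Attachment 7, the 5-week form, contains "Pain with use of device" (none to severe) and a yes/no bleeding item. The rest is comfort and ease of use, willingness to use again or recommend, improvement ratings, symptom visual analogue scales (VAS), the Total Nasal Symptom Score (TNSS) and the NOSE scale. The SNOT-22 in Attachment 8 is due at the same assessment. Neither form has an open question about other problems.

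**The concern.** The plan sets a duty to collect all AEs, but the instrument fielded for the last and longest part of home use does not ask for them. A subject who returns every form complete, and who had a non-serious problem other than pain or bleeding, is given no place to report it as an AE.

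Crusting is the clearest case. Section 12.0 names it as a risk of the device and Section 4.0 excludes people who already have it. Rhinoscopy can show it at week 2, but after that it is neither looked for nor asked about. A skin reaction under the silicone nosepiece is a second case. Section 4.0 excludes "Allergic sensitivity to silicone or any other component of device", but that does not rule out a reaction that first appears during use.

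At stake is how the Aim 3 safety summary can be read. A short AE list for weeks 2 to 4-6 could mean that the device was well tolerated, or that nobody asked.

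**Working it through.** **1. Reproduce the plan's duration.** Section 3.0 gives two home phases: "Subjects will use SinuSonic device twice daily for 3 minutes in the home setting for 14 days" and then "Subjects will continue to use the SinuSonic device twice daily for 3 minutes in the home setting for 2-4 weeks". Total = 2 + 2 = 4 weeks to 2 + 4 = 6 weeks. This agrees with Section 2.0: "The study will take place over the course of 4 to 6 weeks starting with a baseline assessment".

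**2. Share of home use after week 2.** Twice daily is 2 × 7 = 14 sessions a week. Share = sessions after week 2 / all home sessions.

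| Weeks after week 2 | Sessions after week 2 | All home sessions | Share |
|---|---|---|---|
| 2 | 28 | 56 | 50% |
| 3 (the form's 5 weeks) | 42 | 70 | 60% |
| 4 | 56 | 84 | 67% |

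Adding the single clinic session to the denominator changes little: 28/57 = 49.1%, 42/71 = 59.2%, 56/85 = 65.9%.

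**3. What the other visit-4 items can recover.** TNSS scores nasal itching, sneezing and sleep difficulty. The VAS covers pain or pressure and smell. SNOT-22 scores dizziness, ear pain, ear fullness, cough and others. VAS and TNSS ask about one week, which is 1/2 to 1/4 of the 2 to 4 weeks since the clinic visit. The follow-up SNOT-22 states no recall period. NOSE covers a month, but only nasal obstruction, sleep and breathing on exertion. None gives an onset date or a link to device use, and no section turns a worse score into an AE. Crusting and skin reaction are on none of them.

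**4. Illustration of the under-count.** The documents give no AE rate and no capture rate, so both are assumptions here. Take the 40 subjects of Section 5.0, no dropout, independent subjects, and at most one other AE each after week 2. Expected recorded events = 40 × rate × capture. P(empty list) = (1 − rate × capture)^40.

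| Assumed AE rate | Assumed capture | Expected recorded | P(empty list) |
|---|---|---|---|
| 10% (4 events) | 25%, unprompted | 1 | 0.975^40 = 36% |
| 10% | 50%, unprompted | 2 | 0.95^40 = 13% |
| 10% | 90%, asked directly | 3.6 | 0.91^40 = 2% |
| 5% (2 events) | 25%, unprompted | 0.5 | 0.9875^40 = 60% |
| 5% | 50%, unprompted | 1 | 0.975^40 = 36% |
| 5% | 90%, asked directly | 1.8 | 0.955^40 = 16% |

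Only step 2 rests wholly on the documents. Step 4 shows direction and plausible scale, and the assumed capture rates drive the contrast.

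**The case against.** The best reply is that a patient questionnaire is not the whole AE system. Sections 9.0, 11.0 and 19.0 impose a duty to monitor and collect throughout, AE listings are reviewed regularly, and Section 9.0 describes an electronic system that sends alerts. The appendix holds no AE report form for any visit, so it does not show how AEs are recorded, and consent pages are not available to show what subjects are told to report. This stands in part: the plan does not forbid other routes. But listing review and alerts act only on events already recorded, an emailed survey cannot carry out an examination, and no section says how AEs are elicited after week 2.

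A reader might also infer three stronger things that the documents do not support.

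- *That only two possible harms are asked about at visit 4.* TNSS, VAS and SNOT-22 score several other symptoms that could be harms. What is missing is an open item and a route from a score to an AE.
- *That Aim 3 safety will look better than Aim 2 because a clinician's questioning gives way to a two-item checklist.* The 2-week form, Attachment 5, has the same two items and no open question. The documented differences are the in-person visit and rhinoscopy. Clinician questioning about AEs at that visit is plausible but not written down.
- *That the late AE listing will be near-empty by construction.* Unprompted reports remain possible. At a 10% event rate the illustration gives an empty list with probability 13% to 36%. Among the unprompted rows, only a 5% rate with 25% capture makes an empty list more likely than not.

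Finally, this is an exploratory pilot of 40, the objective is secondary, and the point concerns non-serious events in subjects who complete the forms. That limits its weight.

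**Conclusion.** The point holds as a limited gap in safety ascertainment. For 50% to 67% of planned home use, non-serious AEs other than pain and bleeding depend on unprompted reports, and a device risk that the protocol itself names is neither asked about nor examined. The 4-6 week safety summary is therefore likely to under-count such events. The size cannot be fixed from the documents; it depends on AE and capture rates that they do not state. The conclusion also assumes that the forms are used as written and that no unlisted contact takes place after week 2.

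The week-2 visit is in clinic with rhinoscopy and the last assessment is not, so AE counts before and after week 2 should not be compared as if ascertainment were the same. The direction of any resulting bias in that comparison is not established. Sample size, alpha and the efficacy analysis are unaffected. The change is a cheap improvement, worth making.

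**What to change.** Add one item to Attachment 7, and for a uniform method to Attachments 4 and 5:

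*Since the last form (on the 5-minute form: since using the device), have you had nasal crusting, skin irritation, or any other new or worse health problem? Yes / No. If yes: what was it, when did it start, and was it mild, moderate or severe?*

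Enter each Yes in the AE listing that Section 19.0 already presupposes, and state in Section 10.0 that these prompted AEs are tabulated by interval (5 minutes, to week 2, week 2 to the last form).

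The cost is one extra question per form, a little AE coding, and possibly a slightly higher reported AE count. The item makes the questioning uniform but does not replace an examination, so the difference in rhinoscopy before and after week 2 should still be noted when results are reported.

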5.0 Number of Subjects

This is a pilot study. The anticipated study population is 40 subjects.

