10.0 Data Management

All analyses and graphs will be performed with SPSS 24.0, Sample Power 3.0, and Sigma Plot 10.0 (SPSS, Chicago, IL.). Disease information and demographic variables, such as age, gender, race, quality of life (QOL) scores, and VAS scores will be summarized using frequencies, means, and standard deviation as appropriate. Outcome metrics will be compared between baseline and 5 minutes (AIM 1), baseline and 2 weeks (AIM 2), and baseline and 4-6 weeks (AIM 3). Categorical variables will be compared using Chi Square or McNemar's test. Continuous variables will be compared using One-Way ANOVA with repeated measures followed by post-hoc analysis. Data regarding safety and patient satisfaction will be summarized for each time point. A p-value ≤ 0.05 will be considered statistically significant. Due to the exploratory nature of this study, no p-value correction (ie Bonferroni) will be applied. If appropriate, subgroup analysis can be performed based on underlying disease classification (allergic rhinitis, nonallergic rhinitis, CRSsNP, CRSwNP).

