12.0 Risks to Subjects

There is a risk of a loss of confidentiality of your personal information as a result of participation in this study.

There are risks to subjects using the SinuSonic device. Subjects may experience a degree of pain due to use of the device. This degree of pain is unknown. There may also be risk of nose bleeds or crusting around the nasal cavity.

The Rhinoscopy may activate the gag reflex. Additionally, nasal discomfort, nose bleeds, spasms, and coughing may also occur.

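### Nose bleeding is an ungraded Yes/No item with no baseline counterpart and, at weeks 2 and 5, no recall period, so usual bleeds cannot be separated from device-related ones on this item

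*Combined protocol and SAP*

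**What the plan says.** Section 12 lists pain first among the device risks and then adds: "There may also be risk of nose bleeds or crusting around the nasal cavity". Section 4 excludes "History of severe nose bleeding within last 3 months". It also excludes anticoagulation (aspirin is permitted) and nasal crusting or ulceration seen at rhinoscopy.

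Bleeding is recorded as "Bleeding: Yes No" on the 5-minute, 2-week and 5-week forms (Attachments 4, 5 and 7). Attachments 1 to 3, completed at baseline, contain no bleeding item. On the 2-week and 5-week forms the item belongs to a block whose only instruction is "Please rate changes in your nasal symptoms and use of device", with no period stated. On the same forms the visual analogue block begins "OVER THE LAST WEEK, HOW TROUBLESOME HAVE THE FOLLOWING SYMPTOMS BEEN", the TNSS also specifies a week, and the NOSE scale specifies a month. Pain, in the same block as bleeding, has four grades: "Pain with use of device None Mild Moderate Severe".

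Section 10 says that safety data will be reported time point by time point. Section 5 sets the size: "This is a pilot study. The anticipated study population is 40 subjects". No control group is described.

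**The concern.** Without a control group, the only comparator for a subject's bleeding during device use is that subject's own bleeding beforehand, and it is not collected. Someone with occasional mild nosebleeds, or who takes aspirin, is eligible and may answer Yes at week 2 for a bleed that would have happened anyway. Section 12 also lists nose bleeds as a risk of rhinoscopy, which is scheduled at screening and week 2, so the procedure is another possible source of a Yes.

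The missing period adds a second ambiguity. At week 5 a subject could answer for the past week, for the time since the week-2 visit, or for the whole study. Under the last reading, a bleed already reported at week 2 is reported again. Finally, a trace of blood and a heavy bleed give the same answer.

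At stake is whether the bleeding percentages at weeks 2 and 5, which serve the two secondary aims, can be interpreted at all.

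**Working it through.** The plan gives no expected bleeding rate and no basis for the sample size, so there is no figure to reproduce. The calculation below only shows how far the answer depends on the unstated period.

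**Inputs**
- N = 40 (Section 5).
- Background rate *w*, the proportion of subjects with a nosebleed in any week without the device. The documents do not give it; **assumed** 1%, 2%, 5% and 10%.
- Device effect: assumed zero. Weeks are treated as independent.
- The last form is taken at week 5, as Attachment 7 is titled.

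**Formula**
- Probability of a Yes over *k* weeks: 1 − (1 − *w*)^*k*.
- Expected Yes answers: 40 × [1 − (1 − *w*)^*k*].

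**5-week form, by how the subject reads it**

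| *w* per week | Last week (*k* = 1) | Since week 2 (*k* = 3) | Since start (*k* = 5) |
|---|---|---|---|
| 1% | 0.4 | 1.2 | 2.0 |
| 2% | 0.8 | 2.4 | 3.8 |
| 5% | 2.0 | 5.7 | 9.0 |
| 10% | 4.0 | 10.8 | 16.4 |

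For example, at 5%: 40 × (1 − 0.95^3) = 40 × 0.1426 = 5.7, and 40 × (1 − 0.95^5) = 40 × 0.2262 = 9.0. From the narrowest to the widest reading, the expected count rises 4.8-fold at 2% (3.84/0.8) and 4.5-fold at 5% (9.05/2.0), through wording alone.

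**2-week form, read as since start (*k* = 2)**
- At 2%: 40 × (1 − 0.98^2) = 1.6 expected; the chance of at least one Yes is 1 − 0.98^80 = 80%.
- At 5%: 40 × (1 − 0.95^2) = 3.9 expected; the chance of at least one Yes is 1 − 0.95^80 = 98%.
- Over the full assumed range of 1% to 10%: 0.8 to 7.6 expected.

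**Carry-over.** If the 5-week item is read as since start, every subject with a bleed in weeks 0-2 is a Yes on both forms. That is the same 0.8 to 7.6 subjects, with no new event needed.

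**5-minute form.** The single supervised clinic use fixes the period, so these calculations do not apply to it.

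**The case against.** The strongest defence is that the checkbox is not the study's only safety record. Sections 9, 11 and 19 collect adverse events from consent onwards, Section 19 whatever their seriousness or cause, and Section 19 requires follow-up to recovery or stabilisation. Rhinoscopy is scheduled at screening and week 2. The exclusions for severe recent nosebleeds, anticoagulation, crusting and ulceration all lower the background rate. The primary objective concerns a single use, which the 5-minute form covers. This is also an exploratory pilot with descriptive safety reporting, and at 1% to 2% per week only about 0.8 to 1.6 background Yes answers are expected at week 2.

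Much of this stands, and it limits the point. It does not remove it. The adverse-event sections give no severity scale, no method for judging cause, and no link between a Yes and an adverse-event record. The 4-6 week contact is an emailed survey with no rhinoscopy scheduled, so no planned examination supports the last answer. The exclusions lower the background rate without measuring it.

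A reader might also infer more than the documents support:
- *That bleeding is the main device risk.* Section 12 names pain first and ranks nothing.
- *That usual nosebleeds will be counted as device harm.* No section says how a Yes is attributed. The sub-heading about device use on the later forms may invite that reading, or may lead subjects to report only bleeding during use; neither is stated.
- *That a planned McNemar test lacks its baseline value.* Section 10 says "Outcome metrics will be compared between baseline and 5 minutes (AIM 1), baseline and 2 weeks (AIM 2), and baseline and 4-6 weeks (AIM 3", but treats safety separately, as a summary at each time point. It commits to no paired test of bleeding.
- *That one bleed will be counted twice.* With separate summaries it is carry-over. It becomes double counting only if time points are added together.
- *That the study cannot see bleeding severity.* That is true of this item, not of the adverse-event record.

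**Conclusion.** The point holds as a defect in how one named device risk is measured at weeks 2 and 5. On this item, usual bleeds cannot be separated from device-related ones, the period covered by the week-5 answer is undefined, and a bleed in weeks 0-2 may reappear at week 5. The primary, single-use aim is little affected.

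The size depends on a background rate that the documents do not give. With no device effect, the expected week-5 count ranges from 0.8 to 3.8 of 40 at an assumed 2% per week, and from 2.0 to 9.0 at 5%, according to how the question is read. These figures assume a constant weekly rate and independent weeks. They illustrate sensitivity and do not predict the result. The absence of a baseline item, a grade and a period is plain on the forms and needs no assumption.

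**What to change.** - **Baseline.** Add to Attachment 2 one nose-bleeding item with a fixed 2-week look-back, graded None/Mild/Moderate/Severe like the pain item.
- **Weeks 2 and 5.** Use the same grades on Attachments 5 and 7, with the period worded as *since your last study form*.
- **Reporting.** Give, descriptively and per time point, the number of subjects with new or worsened bleeding relative to baseline. Report bleeding after week 2 separately and state that its window is 2 to 4 weeks.
- **Testing, if wanted.** Any versus no bleeding can be compared with baseline by McNemar's test at week 2, where both windows are two weeks. The test needs the grades collapsed to two levels. It will also be weak: if all changes go one way, the exact two-sided test needs six of them (2 × 0.5^6 = 0.031; five give 2 × 0.5^5 = 0.063). The descriptive count should lead.

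The cost is one added baseline line and two reworded items, with no extra visit. The drawback is that the 2-week look-back does not exactly match the later window. At an assumed 5% per week, a 2-week window expects 3.9 of 40 and a 4-week window 7.4 with no device effect, so bleeding after week 2 should not be read as a like-for-like change from baseline. Baseline bleeding that is not recorded cannot be reliably recovered later, so the item has to be in place before enrolment.
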